7.2 Secondary Endpoints

Secondary efficacy assessment includes recurrence (after EoT) and survival.

The percentage of subjects with a recurrence of the baseline fungal infection 42 days after EoT (Week 6 Follow up) as determined by the DRC will be presented with 95% CIs for the ITT and PP populations using the same approach as for the primary endpoint. Recurrence is defined as global success at EoT but re-emergence of the baseline *Candida auris* infection during the post treatment follow-up. Re-emergence of the *Candida auris* infection is required to be with the same species and involving the same site that was initially identified at Screening/Treatment Day 1.

The percentage of subjects surviving at the defined time points will be presented for the ITT and PP populations. A Kaplan Meier plot will also be produced summarizing the survival curve over time and the median time to death. A subject without a reported death will be censored at the point of last time the subject was known to be alive. The probability of survival will be calculated at 42 and 84 days after Day 1 (first dose of study drug).

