20.0 Analytical Plan

All statistical processing will be performed using SAS[®] version 9.3 or later, unless otherwise stated.

Descriptive statistics (i.e., number of subjects, mean, standard deviation, median, minimum, maximum) will be presented for all continuous variables; number and

percentage of subjects will be presented for categorical variables. For parameters measured over time, observed data and changes from baseline will be described for each time point.

All analyses of the study results for SCY-078 will be descriptive. Unless otherwise stated, data will be analyzed as is with no imputation.

A Statistical Analysis Plan (SAP) describing all statistical analyses in detail will be provided as a separate document.

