The purpose of this SAP is to ensure the statistical methodologies that will be used are complete and appropriate to allow valid conclusions regarding the study objectives. Results obtained from the analyses outlined in this document will be the basis of the final clinical study report (CSR) for this protocol. Changes made to the SAP after it has been signed but prior to database lock will be documented in a SAP amendment. Changes made to the analyses after database lock will be described in the CSR. Additional exploratory analyses which aren't listed in the protocol are planned as outlined in Section 7.3.1. Table shells and data set specifications will be prepared on the basis of this document.

2. Study Objectives

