b. PK testing will be conducted for subjects who give their consent to participate in the PK portion of the study (the PK Subset). Sparse PK samples for Population PK analysis will be collected at the following visits and sampling windows: on Treatment Day 2 (one sample collected anytime post dosing); between Treatment Days 3 to 5 (one sample collected predose on any of these days) and between Treatment Days 7 to 10 (one sample collected predose). The time of dosing and sample collection must be recorded on the subject diary and eCRF.

c. All enrolled subjects will receive an initial oral loading dose of 750 mg of SCY-078 (3 tablets of 250 mg) BID during the first 2 days of treatment and then subsequent oral doses of 750 mg QD for up to 90 days.

Table 1	Schedule of Survival Visits and Procedures (Study
	SCY-078-305)

PROCEDURE Visit	Visit/contact Survival Day 42	Visit/contact Survival Day 84
Days (allowable window)	± 2	± 2
Subject Status (alive/ deceased)	х	х

3. General Statistical Considerations

Continuous data will be described using descriptive statistics (i.e. number of subjects, mean, standard deviation (SD), median, minimum, and maximum). Categorical data will be described using the subject count and percentage in each category. For the summary statistics of all numerical variables unless otherwise specified, minimum and maximum will be displayed to the same level of precision as reported. Mean and median will be displayed to one level of precision greater than the data collected. Standard deviation / standard error will be displayed to two levels of precision greater than the data collected. P-values will be rounded to three decimal places. If a p-value is less than 0.001 it will be reported as "<0.001." If a p-value is greater than 0.999 it will be reported as ">0.999." Data will be displayed in all listings sorted by disease category.

Unless otherwise specified, baseline will be defined as the last non-missing assessment prior to or on the date (and time if appropriate) of the first dose of study drug. Change from baseline is defined as: post-baseline value – baseline value. For parameters measured over time, observed data and changes from baseline will be described for each time point.

The study day will be calculated as follows:

If the assessment date occurs on or after the date of the first dose of study drug:

Study day = assessment date - first dose date + 1.

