7.1.1 Primary Analysis

The primary efficacy analysis will be performed at EoT. A responder analysis will be performed on the number and percentage of subjects with Successful Global Response as determined by the DRC will be presented with a 95% confidence interval (CI) for a single binomial proportion in the ITT and PP populations. The Clopper Pearson method will be used for the confidence interval. If Global Response has not been deemed a success or failure, the outcome will be categorized as not evaluable. A responder is defined as a subject with either a success or a failure. A response of not evaluable will not be included in the analysis.

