7.3 Exploratory Endpoints

Exploratory categorical endpoints will be presented with 95% CIs for the ITT and PP populations using the same approach as for the primary endpoint.

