7.3.1 Exploratory Analyses

A responder analysis will be performed on the following endpoints. If the outcome cannot be assessed due to missing data, it will be categorized as not evaluable. A responder is defined as a subject with a response other than not evaluable. A response of not evaluable will not be included in the analysis.

- Percentage of subjects for each global response (complete response, partial response, stable disease, progressive disease) EoT, as determined by the DRC
- Percentage of subjects with clinical success at EoT, as determined by the investigator and DRC
- Percentage of subjects for each clinical response (complete response, partial response, stable response, progression of fungal disease, death) at EoT, as determined by the DRC

- Percentage of subjects with mycological success at EoT, as determined by the investigator and DRC
- Percentage of subjects with global success at EoT, as determined by the investigator

Additional exploratory analyses:

- All cause mortality at Day 30
- Analysis of response by minimum inhibitory concentration (MIC) based on CLSI M27-A3 *in vitro* method and EUCAST method at Screening

The following exploratory analyses were not originally included in the protocol:

- Evidence of ongoing infection at Baseline as determined by the DRC
- Causal relationship of death in the opinion of the DRC (if death is reported at any time during the study)
- Global response by site of infection (candidemia only, Pleural/Pulmonary, Intraabdominal/Pelvic, Soft tissue/wound, Bone and joint, Urinary tract, other)
- Global response by reason for enrollment (primary, refractory, intolerance to SOC, stepdown)
- Global response by region (India, Pakistan, South Africa)
- Global response by Age (,65; >= 65 years)
- Global response by neutropenia (ANC < 500) vs non neutropenic

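### SAP 7.2 sets no at-risk denominator for recurrence: only EoT successes can recur, yet the stated populations and approach appear to keep EoT failures in

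*SAP*

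**What the plan says.** **Who can recur.** SAP 7.2 states: "Recurrence is defined as global success at EoT but re-emergence of the baseline" infection, with the same species and site as at baseline. Protocol 20.7.1.2 has the same definition. A subject who fails at EoT therefore cannot be a recurrence.

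**Who is counted.** SAP 7.2 says that the percentage "as determined by the DRC will be presented with 95% CIs for the ITT and PP populations", and refers to the primary endpoint for the approach. Protocol 20.7.2 also names only the ITT and PP populations. SAP 3.2 defines ITT as all enrolled subjects. PP requires an EoT assessment, at least 10 days of study drug and no major violation, but not EoT success.

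**What the primary approach is.** SAP 7.1.1 uses a single binomial proportion with a Clopper-Pearson interval. On the denominator it says: "A responder is defined as a subject with either a success or a failure". Only not-evaluable outcomes are left out. SAP 7.3 presents the exploratory endpoints "using the same approach as for the primary endpoint", and 7.3.1 spells out the rule for them: "A responder is defined as a subject with a response other than not evaluable".

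**Where the detail belongs.** Protocol 20.0 says: "A Statistical Analysis Plan (SAP) describing all statistical analyses in detail will be provided as a separate document". The SAP Introduction says: "Table shells and data set specifications will be prepared on the basis of this document". The list of tables is kept outside the SAP (section 10).

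**What is absent.** Neither document restricts the recurrence denominator to EoT successes, codes an EoT failure for recurrence, or says how an EoT success who dies before Week 6 is counted.

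**The concern.** A recurrence rate is normally read as the risk of relapse among those who responded. If subjects who cannot relapse stay in the denominator, the figure becomes the share of all evaluable subjects who respond and then relapse. That is a legitimate quantity, but a different one, and it mixes two outcomes. The more subjects fail at EoT, the fewer can recur, so poorer efficacy pulls the recurrence percentage down. One reported value can then stand for quite different relapse risks, and its interval looks more precise than the number at risk supports.

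Recurrence at Week 6 is a stated secondary efficacy objective. In an open-label study the denominator is best written down before database lock, so that it is not chosen with the results in view.

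**Working it through.** The documents give no expected success or recurrence rate, so there is no figure of theirs to reproduce. The only input taken from them is the planned enrolment of about 30 (SAP 3.1). All other counts are assumed for illustration.

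**Point estimate.** Let R be the recurrences, S the EoT successes and F the EoT failures kept in the denominator.

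- All-subject reading: R/(S + F)
- Among successes: R/S
- Ratio of the first to the second: S/(S + F), which is below 1 whenever F is at least 1. The estimates themselves differ only if R is also at least 1.

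**Interval.** The Clopper-Pearson 95% limits for x out of n are the 2.5% quantile of Beta(x, n − x + 1) and the 97.5% quantile of Beta(x + 1, n − x). For x = 0 the upper limit is 1 − 0.025^(1/n).

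| Assumed counts (S + F = 30) | All-subject reading | Among EoT successes |
|---|---|---|
| R = 3, S = 27 | 3/30 = 10.0% (2.1 to 26.5) | 3/27 = 11.1% (2.4 to 29.2) |
| R = 3, S = 15 | 3/30 = 10.0% (2.1 to 26.5) | 3/15 = 20.0% (4.3 to 48.1) |
| R = 3, S = 9 | 3/30 = 10.0% (2.1 to 26.5) | 3/9 = 33.3% (7.5 to 70.1) |
| R = 0, S = 15 | 0/30 = 0% (upper limit 11.6) | 0/15 = 0% (upper limit 21.8) |

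The first three rows would be reported identically. The gap is small when nearly everyone responds, twofold at 50% success and threefold at 30%.

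**Dropping not-evaluable subjects does not close the gap.** With 18 successes, 9 failures, 3 not evaluable at EoT and 3 recurrences, the all-subject reading gives 3/27 = 11.1%, against 3/18 = 16.7% among successes.

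**Unknown Week 6 status.** Take 15 successes, 15 failures, 4 recurrences and 3 successes who die or are lost without documented recurrence. Four treatments are possible:

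- all-subject reading with those 3 dropped: 4/27 = 14.8% (4.2 to 33.7)
- all successes, documented recurrences only: 4/15 = 26.7% (7.8 to 55.1)
- successes of known status only: 4/12 = 33.3% (9.9 to 65.1)
- all successes, unknown counted as recurrence: 7/15 = 46.7% (21.3 to 73.4)

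Among EoT successes, the second and fourth bound what the data can support, and the third lies between them.

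**The case against.** The strongest reply is that the cross-reference in SAP 7.2 follows directly on the mention of confidence intervals, so it may import only the Clopper-Pearson method. SAP 7.3 uses the same phrase, yet 7.3.1 then restates the evaluability rule, which would be unnecessary if the phrase already carried it. SAP 7.2 has no such restatement, and success or failure in 7.1.1 describes EoT response, not recurrence. This stands as far as it goes. It makes the direction of the error conditional, but it does not supply a denominator. The populations named are still ITT and PP, and both can contain EoT failures.

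A second reply is that the protocol asks for a percentage of subjects, and that a responder-only rate conditions on a post-baseline outcome. That is fair. It supports keeping an all-subject figure under its own label, but not leaving the reader to guess which figure is shown.

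A third reply is that little depends on it. The endpoint is secondary, the protocol calls all analyses descriptive, and no decision rule uses it. SAP section 3 says: "Categorical data will be described using the subject count and percentage in each category". The number of EoT successes is reported under 7.1.1, so the crude ratio can be rebuilt. This also stands and limits the severity. The printed interval and the handling of unknown-status successes would still be unspecified.

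A reader might go further and infer that the SAP prescribes coding EoT failures as free of recurrence, so that the reported rate will certainly be too low. The documents do not support that: no sentence codes an EoT failure for recurrence, and the point estimate is unaffected if there are no recurrences or no failures.

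**Conclusion.** The point holds in a conditional form. The definition confines recurrence to EoT successes, while the stated populations and the referenced approach, read as written, leave EoT failures in the denominator. On that reading the estimate is S/(S + F) times the rate among successes. With assumed counts this means half the rate at 50% success and nine tenths of it at 90%. With no recurrences the estimate is unchanged but the interval is too narrow for the number at risk. If the cross-reference imports only the interval method, the defect is an unstated denominator of unknown direction.

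The consequence is modest. It concerns how one secondary, descriptive percentage is read. It touches neither the primary endpoint nor any test. The threefold gap needs a 30% success rate, for which the documents give no basis. It is still worth correcting, because the present text can yield different rates and intervals from the same data.

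**What to change.** In SAP 7.2, replace the cross-reference with an explicit rule:

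- **Main analysis.** Subjects with DRC-determined recurrence, divided by all subjects in ITT (and separately PP) with DRC-determined global success at EoT, with a Clopper-Pearson 95% CI.
- **Same table.** The number of EoT successes, of deaths before Week 6 without documented recurrence, and of missing Week 6 assessments.
- **Sensitivity analyses.** (a) The rate among EoT successes with a Week 6 assessment. (b) The rate over all EoT successes with those of unknown status counted as recurrences. State what counts as a Week 6 assessment, since culture, imaging and serology at that visit are done only if applicable.
- **Optional.** Keep an all-subject percentage, labelled as the share of subjects who responded and then relapsed.

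The main analysis in effect treats unknown status as no recurrence, so it is a lower bound; this is why both sensitivity analyses are needed. Its denominator has one further advantage. Protocol 20.4 counts a missing EoT assessment as failure, whereas SAP 7.1.1 excludes it as not evaluable, but the set of EoT successes is the same under either rule.

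The cost is one SAP paragraph and one table shell. No protocol change or new data are needed, and the SAP Introduction already provides for amendment before database lock. The price is a smaller n, a wider interval and a less favourable figure.

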7.3 Exploratory Endpoints

Exploratory categorical endpoints will be presented with 95% CIs for the ITT and PP populations using the same approach as for the primary endpoint.

7.3.1 Exploratory Analyses

A responder analysis will be performed on the following endpoints. If the outcome cannot be assessed due to missing data, it will be categorized as not evaluable. A responder is defined as a subject with a response other than not evaluable. A response of not evaluable will not be included in the analysis.

- Percentage of subjects for each global response (complete response, partial response, stable disease, progressive disease) EoT, as determined by the DRC
- Percentage of subjects with clinical success at EoT, as determined by the investigator and DRC
- Percentage of subjects for each clinical response (complete response, partial response, stable response, progression of fungal disease, death) at EoT, as determined by the DRC

- Percentage of subjects with mycological success at EoT, as determined by the investigator and DRC
- Percentage of subjects with global success at EoT, as determined by the investigator

Additional exploratory analyses:

- All cause mortality at Day 30
- Analysis of response by minimum inhibitory concentration (MIC) based on CLSI M27-A3 *in vitro* method and EUCAST method at Screening

The following exploratory analyses were not originally included in the protocol:

- Evidence of ongoing infection at Baseline as determined by the DRC
- Causal relationship of death in the opinion of the DRC (if death is reported at any time during the study)
- Global response by site of infection (candidemia only, Pleural/Pulmonary, Intraabdominal/Pelvic, Soft tissue/wound, Bone and joint, Urinary tract, other)
- Global response by reason for enrollment (primary, refractory, intolerance to SOC, stepdown)
- Global response by region (India, Pakistan, South Africa)
- Global response by Age (,65; >= 65 years)
- Global response by neutropenia (ANC < 500) vs non neutropenic

7.3.2 Clinical and Mycological Outcome

Clinical success is defined as a complete clinical response (the resolution of all clinical signs and symptoms and/or radiological abnormalities from baseline attributable to the *Candida auris* infection) or a partial clinical response (major improvement of all clinical signs and symptoms and/or radiological abnormalities from baseline attributable to the *Candida* auris infection).

Mycological success is defined as a mycological response (mycological clearance (direct and/or negative cultures [when obtainable] and/or normal serological results [when appropriate]).

8. Safety

The safety analyses will be performed on all subjects in the safety population. Analyses will be based on physical exam, vital signs, 12-lead ECGs, safety laboratory tests (hematology, blood chemistry and urinalysis), concomitant medications, AEs and treatment discontinuations. Safety analyses in general will be descriptive and will be presented in tabular format with the appropriate summary statistics.

Individual subject listings will be provided to support the tables.

8.1 Adverse Events

All AE summaries will be restricted to treatment-emergent AEs (TEAEs) only. A TEAE is defined as any event not present before exposure to study drug or any event already present that worsens in either intensity or frequency after exposure to study drug.

For the purpose of inclusion in TEAE tables, incomplete AE start and end dates will be imputed as follows:

Missing onset dates (where UK and UNK indicate unknown or missing day and month respectively):

- UK-MMM-YYYY: If the month and year are different from the month and year of the date of first dose, assume 01-MMM-YYYY. If the month and year are the same as the month and year for the date of first dose, and the end date (after any imputation) is on or after the date of first dose, then assume the date of first dose. If the month and year are the same as the date of first dose, and the end date (after any imputation) is prior to the date of first dose, then assume the end date for the start date.
- DD-UNK-YYYY/UK-UNK-YYYY: If the year is different from the year of the date of first dose, assume 01-JAN-YYYY of the collected year. If the year is the same as the date of first dose year, and the end date (after any imputation) is on or after the date of first dose, then assume the date of first dose. If the year is the same as the date of first dose, and the end date (after any imputation) is prior to the date of first dose, then assume the end date.

Missing end dates (where UK and UNK indicate unknown or missing day and month respectively):

- UK-MMM-YYYY: Assume the last day of the month;
- DD-UNK-YYYY/UK-UNK-YYYY: Assume 31-DEC-YYYY.

All adverse events will be classified by SOC and PT according to the Medical Dictionary for Regulatory Activities (MedDRA, March 2023 Version). An overview summary of the number and percentage of subjects with any TEAE, serious TEAE, treatment-related TEAE, treatment-related serious TEAE, TEAE leading to study treatment discontinuation, TEAE leading to study discontinuation, and AE leading to death will be provided.

All AEs will be presented in a listing.

8.1.1 Treatment-Emergent Adverse Events

Summaries of the total number of TEAEs and the number and percentage of subjects with at least one TEAE will be provided. Treatment-emergent AEs will be presented by SOC and PT. At each level of subject summarization, a subject is counted once if the subject reported one or more events. Percentages will be calculated out of the number of subjects in the safety population.

The summary of TEAEs will be presented in alphabetical order of SOC. Within each SOC, PTs will be sorted in descending order from the PT with the highest total to the PT with the lowest total frequency. If the total frequency for any two or more PTs is equal, the PTs will be presented in alphabetical order.

The summarization described above will also be repeated for the following:

- Serious Adverse Events;
- Treatment-Related Adverse Events;
- Treatment-Related Serious Adverse Events;
- Adverse Events Leading to Dose Interruption.

8.1.2 Related Adverse Event to Study Treatment

A summary of related TEAEs to study treatment will be presented in a table. The investigator will provide an assessment of the relationship of the event to the study treatment. Related AEs are those reported as "Possibly Related", "Probably Related", or "Related". If a subject reports multiple occurrences of the same TEAE, only the most closely related occurrence will be presented. Treatment-emergent AEs that are missing a relationship will be considered "Related" and be presented in the summary table but will be presented in the data listing with a missing relationship. Percentages will be calculated based on the number of subjects in the safety population.

The TEAE data will be categorized and presented by SOC and PT in a manner similar to that described in Section 8.1.1.

Related treatment-emergent SAEs to study treatment will also be presented in a table. Treatmentemergent SAEs that are missing a relationship will be presented in the table as "Related" but will be presented in the data listing with a missing relationship.

